6.16.2.7. Duration of Hospitalization

Treatment comparisons of the mean DOH (in days) will be compared between active treatment and placebo will be made using nonparametric rank-sum test (such as Mann-Whitney or van Elteren test).

6.16.2.8. Time to Admission to ICU

Time to ICU is defined (in days) as:

(First study day when ICU status is changed to "Yes" – Infusion Date +1)

If a patient has been admitted to the hospital or ICU by completion or early discontinuation of study/study treatment, the patient will be censored at the date of their last visit during the treatment and assessment period.

Time to ICU will be summarized by treatment group for those patients who are admitted to the ICU.

Time to ICU may be presented graphically.

6.16.2.9. Proportions of Participants Hospitalized, Admitted to the ICU, Requiring Mechanical Ventilation

The proportion of participants hospitalized, admitted to the ICU, requiring mechanical ventilation (oxygen source = "Intubation/Mechanical Ventilation") will be summarized separately by treatment group. These endpoints will be evaluated thru Days 7, 11, 15, 22, and 29.

If an event (hospitalization, ICU, or Mechanical Ventilation) occurs, the participant will be defined as having had the event for all subsequent timepoints evaluated. For example, if a participant experiences a hospitalization on day 8, their hospitalization status would be defined as:

- 'No' for the evaluation of hospitalization thru day 7, and
- 'Yes' for hospitalization thru Days 11, 15, 22, 29.

No imputation will be used as these endpoints are based on running records; i.e., an event is only reported if they are observed.

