Treatment comparisons of continuous efficacy, and pharmacodynamic variables with multiple postbaseline measurements will be made using a mixed-effects model repeated measures (MMRM) analysis. When MMRM is used, it includes: (a) treatment group, (b) baseline value in the model, (c) visit, and (d) the interactions of treatment-by-visit as fixed factors. The covariance structure to model the within-patient errors will be unstructured. If the unstructured covariance matrix results in a lack of convergence, the heterogeneous Toeplitz covariance structure, followed by the heterogeneous autoregressive covariance structure, will be used. The first structure to yield convergence will be used for inference. The Kenward-Roger method will be used to estimate the denominator degrees of freedom. Type III sums of squares for the least-squares (LS) means will be used for the statistical comparison; the 95% confidence interval (CI) will also be reported. Unless otherwise specified, for MMRM, reported data from only planned visits will be used as the primary analysis.

Treatment comparisons of continuous efficacy, safety, and health outcome variables with a single postbaseline timepoint will be made using analysis of covariance (ANCOVA) with: (a) treatment group, and (b) baseline value in the model. Type III sums of squares for LS means will be used for statistical comparison between treatment groups. The LS mean difference, standard error, p-value, and 95% CI, unless otherwise specified, will also be reported. Missing data imputation method for the ANCOVA model is specified in Section 6.3.

Treatment comparisons for binary endpoints will be made using logistic regression with a Firth penalized likelihood (Firth 1993). The model will include the treatment groups. The Firth correction can be implemented in PROC Logistic by including 'firth' as an option in the model statement. The odds ratio and the corresponding CIs, as well as the treatment differences and the corresponding CIs, will be reported. If the number of observed events is less than 5 in any treatment arm an exact test (i.e., Fisher's exact) will be conducted instead of using a logistic regression.

The Kaplan-Meier (KM) product limit method will be used for time-to-event analyses. The hazard ratio and log-rank test will be reported. Time for all analyses will be described in units of days.

For all change from baseline analyses, patients who do not have a valid baseline measure will be excluded.

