6.10.3.3. Participant Clinical Status

6.10.3.3.1. COVID-19-Related Hospitalization or Death from Any Cause

Proportion (percentage) of participants who experience any of the following by Day 29 will be analyzed:

- COVID-19-related hospitalization (defined as ≥24 hours of acute care), or
- Death from any cause

The proportion of participants that experience hospitalization or death from any cause by Day 29 will be summarized by treatment in frequency tables and listed.

In addition, the number of participants that experience COVID-19 hospitalization or death from any cause by Day 29 will be analyzed using logistic regression to compare active treatment versus placebo at each dose level. If the number of observed events is less than 5 in any treatment arm an exact test (i.e. Fisher's exact) will be conducted instead of using a logistic regression. Data will not be imputed due to dropouts or missing data.

Proportion (percentage) of participants who experience COVID-19 related hospitalization or death from any cause by Days 22, 60, and 85 will also be analyzed.

The safety population will be utilized to analyze COVID-19-related hospitalization or death from any cause.

Based on the 'Hospitalization Events' eCRF page, a COVID-19-related hospitalization event is defined as an event with:

'Reason for Health Care Visit' of 'Primary Study Condition'

AND

- a 'Health Care Service Type' of:
 - o 'General Ward' or 'ICU'

OR

o 'Emergency Room' with a duration of \ge 24 hours.

6.10.3.3.1.1. Bayesian Modeling for COVID-19-Related Hospitalization or Death From Any Cause

Additionally, a Bayesian sensitivity analysis will be performed. A Bayesian logistic regression model will be fitted to evaluate the success criteria by the Lilly statistics group with the model listed below:

$$r_{ij} \sim Binomial(p_{ij}, 1)$$

$$\log\left(\frac{p_{ij}}{1 - p_{ij}}\right) = \alpha_i$$

Where,

 r_{ij} : is 1 if patient j on treatment i was hospitalized and 0 otherwise α_i : a parameter corresponding to treatment i (with i=1 being the placebo group). and priors:

$$\alpha_1 \sim \pi(\alpha_1)$$

At least 2 priors $(\pi(\alpha_1))$ will be considered for α_1 , a diffuse $N(0,100^2)$ and an informative prior based on available information at the time of analysis.

The safety population will be utilized to analyze COVID-19-related deterioration.

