6.16.2.6. Time to Hospitalization

Time to Hospitalization is defined (in days) as:

(First study day when hospitalized status is changed to "Yes" – Infusion Date +1)

If a patient has been admitted to the hospital or ICU by completion or early discontinuation of study/study treatment, the patient will be censored at the date of their last visit during the treatment and assessment period.

Time to hospitalization will be evaluated during the study treatment and assessment period only and will be summarized by treatment and listed. Cox proportional hazard model will be used.

Time to hospitalization may be presented graphically.

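### Time to ICU is summarised only among participants who reach the ICU, so it is not a randomised comparison and cannot show that admissions were prevented

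*SAP*

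**What the plan says.** SAP section 6.16.2.8, one of the additional exploratory analyses not defined in the protocol, counts time to ICU in days from infusion. Its only instruction for a summary is "Time to ICU will be summarized by treatment group for those patients who are admitted to the ICU". A plot is optional, with no population named: "Time to ICU may be presented graphically".

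The same section has a censoring rule. Its trigger is "If a patient has been admitted to the hospital or ICU by completion or early discontinuation of study/study treatment" and its consequence is "the patient will be censored at the date of their last visit during the treatment and assessment period".

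Three other places bear on this:

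- Section 6.1.4 sets the default: "The Kaplan-Meier (KM) product limit method will be used for time-to-event analyses", followed by "The hazard ratio and log-rank test will be reported".
- Section 6.16.2.6 has the same censoring sentence but does not restrict the set to those hospitalised: "Time to hospitalization will be evaluated during the study treatment and assessment period only and will be summarized by treatment and listed". It adds a Cox model.
- Section 6.16.2.9 reports the proportion admitted to the ICU by treatment group through Days 7, 11, 15, 22 and 29, with a participant's event status carried forward.

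**The concern.** Two things are wrong with the section as it stands.

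First, the analysis set is defined by the outcome. Setting ICU-admitted participants on active treatment beside ICU-admitted participants on placebo compares those whom the drug did not protect with a different mix of patients. Randomisation no longer balances the groups. Participants in whom admission was prevented are absent, so prevention, the effect of most interest, cannot appear.

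Second, the restriction and the censoring rule cannot both operate. Censoring is for participants without the event, and an admitted-only set has none.

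At stake is a by-treatment summary that may show nothing when the drug works, or may point the wrong way.

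**Working it through.** The SAP states no ICU rate, event count or power for this endpoint, so there is no figure to reproduce. The event days, risks and hazard ratios below are assumptions. Only the arm size of 122 comes from the SAP (section 5.2, Arms 9-11).

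**Step 1: the censoring sentence.** There are two readings.

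- As printed, the trigger is having been admitted to hospital or ICU. In an admitted-only set every participant meets it, so everyone is censored and there are no events.
- With a missing *not* restored, nobody in an admitted-only set meets it, so the rule is idle.

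The second reading is probably what was meant. The censoring rules in 6.10.3.1.6, 6.10.3.2.2 and 6.10.3.2.7 all apply to participants who have *not* had the event. Section 6.16.2.6 has the same apparent slip. Even with *not* restored, naming both hospital and ICU leaves the ICU endpoint without a rule for someone admitted to a ward but never to the ICU.

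**Step 2: a small example, 122 per arm.** Placebo admissions fall on Days 3, 4, 5, 8, 10, 12, 14 and 16. Active treatment prevents the last five, leaving Days 3, 4 and 5.

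- Admitted only: the placebo median is (8 + 10)/2 = 9 days and the active median is 4 days. With admissions as events, the placebo curve reaches 100% on Day 16 and the active curve on Day 5.
- All participants: cumulative incidence is 8/122 = 6.6% on placebo and 3/122 = 2.5% on active. The curves coincide to Day 5, after which active stays lower.

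Active treatment prevented five of eight admissions and caused none, yet the admitted-only median is five days earlier.

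**Step 3: does the direction depend on when the drug acts?** Take a constant placebo hazard h = −ln(1 − R)/29, where R is the placebo ICU risk to Day 29. Risk to time t is F(t) = 1 − exp(−H(t)), where H is the cumulative hazard. The median m among those admitted solves F(m) = F(29)/2.

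For R = 5%, h = 0.0513/29 = 0.00177.

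- Late-acting (hazard ratio 1 to Day 5, then 0.1): H(29) = h(5 + 0.1 × 24) = 7.4h = 0.0131, so the risk is 1.30%. Half of that is reached at H = 0.00652, which gives m = 3.7 days.
- Even (hazard ratio 0.3 throughout): H(29) = 0.3 × 29h = 8.7h = 0.0154, so the risk is 1.53% and m = 14.4 days.
- Early-acting (hazard ratio 0.1 to Day 5, then 1): H(29) = h(0.1 × 5 + 24) = 24.5h = 0.0433, so the risk is 4.24% and m = 16.6 days.

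Each cell gives the ICU risk to Day 29, then the median days among those admitted:

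| Placebo | Late-acting | Even | Early-acting |
|---|---|---|---|
| 1%; 14.5 | 0.26%; 3.7 | 0.30%; 14.5 | 0.85%; 16.7 |
| 3%; 14.4 | 0.77%; 3.7 | 0.91%; 14.5 | 2.54%; 16.7 |
| 5%; 14.3 | 1.30%; 3.7 | 1.53%; 14.4 | 4.24%; 16.6 |
| 10%; 14.1 | 2.65%; 3.7 | 3.11%; 14.4 | 8.52%; 16.5 |

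In every scenario the active cumulative risk never exceeds placebo at any time to Day 29. The admitted-only median nevertheless moves earlier, hardly moves or moves later, according to the timing of the effect.

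**The case against.** The strongest defence is that this is a description and not a comparison. Section 6.16.2.8 omits the Cox sentence found in 6.16.2.6, the endpoint is exploratory, and Arms 12-14 are descriptive throughout. Section 6.16.2.9 also puts the ICU proportions by arm alongside, at five timepoints, so a reader would see the risk next to any median. Much of this stands and keeps the stakes low. It does not settle the matter. The summary is laid out by treatment group, the default in 6.1.4 still calls for a hazard ratio and log-rank test in time-to-event analyses, and the proportions do not resolve the conflict with the censoring sentence.

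A reader might also infer three stronger points, which the SAP does not support:

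- *Every arm's curve must end at 100%.* The plot is optional and its population is unstated. The 100% end point follows only if the plot uses the admitted-only set with admissions counted as events. An arm with no admission has no curve, and the censoring sentence applied literally would leave no events at all.
- *Benefit will look like harm.* In the scenarios tried, the reversal appears only when protection comes late; even and early protection do not produce it.
- *Time to hospitalisation is wrong because it leaves out death.* It is a component endpoint under its own name. Hospitalisation or death from any cause is already analysed by Days 22, 29, 60 and 85 in 6.10.3.3.1, where "The safety population will be utilized to analyze COVID-19-related hospitalization or death from any cause". Adding death to 6.16.2.6 would be a different endpoint, not a correction.

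**Conclusion.** The point holds as a minor one. The admitted-only restriction conditions on the outcome, so the by-treatment summary has no randomised interpretation and cannot show prevention of ICU admissions. It also cannot be reconciled with the section's own censoring rule on either reading. Both conclusions follow from the text and need no assumed rates.

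The size does rest on assumptions. Across placebo ICU risks of 1% to 10%, the admitted-only median moves from about 14 days to 3.7 days, hardly at all, or to about 16.5 to 16.7 days, depending on when the drug acts. Few participants would be involved: at 5% risk and 122 per arm, about 6.1 admissions are expected on placebo (0.05 × 122) and 1.6 on a late-acting drug (0.0130 × 122). No primary or secondary conclusion depends on this endpoint, and 6.16.2.9 already gives the risk by arm.

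**What to change.** In SAP section 6.16.2.8:

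1. Delete the restriction to admitted participants. Analyse time to first ICU admission in all treated participants (the safety population), with ICU admission as the event.
2. Correct the censoring sentence so that those not admitted to the ICU are censored at their last visit in the treatment and assessment period, and make ICU admission alone the trigger.
3. State how death before ICU admission is handled, for example as a competing event.
4. State that any plot uses the same population.
5. Keep the times of those admitted as a descriptive listing.

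In section 6.16.2.6, correct the same censoring sentence and leave the definition of time to hospitalisation otherwise unchanged.

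The cost is a few sentences of SAP text and a routine program change. No new data are needed.

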6.16.2.10. Days Since Symptom Onset Cutpoint Analysis

An exploratory cutpoint analysis may be performed to determine the number of days since symptom onset maximizes the change from baseline to Day 11 (±4 days) in SARS-CoV-2 viral load between treatment with active treatment and placebo.

6.16.2.11. SpO2 Measurements of Interest

The proportion of participants experiencing an SpO₂ measurement of interest (<96%, $\ge 96\%$), (<92%, $\ge 92\%$) through Day 11 and through Day 29 will be evaluated separately using a logistic regression analysis with treatment as a fixed effect and baseline SpO₂ as a covariate in the model. Missing values will be considered to be missing completely at random (MCAR).

6.16.2.12. Viral Load Plots

The 7th octile (87.5th percentile) for the observed viral load data will be plotted across Days 1, 3, 5, 7, and 11 for all Treatment Arms. Additionally, the 4th (median), 5th (62.5th percentile), and 6th (75th percentile) octiles will be plotted separately.

The 4th, 5th, 6th, and 7th octile for viral load data adjusted for days from symptom onset at baseline will be plotted across Days 1, 3, 5, 7, and 11 for all Treatment Arms. Viral load participant data will be adjusted by multiplying the participants number of days from symptom onset at baseline by 0.158 (estimated mean daily decrease in viral load) and then adding the result to all of the participants non-zero viral load measurements. Note, that if the observed viral load is zero, it will not be adjusted.

6.16.2.13. Variants

Baseline and treatment-emergent variants may be identified, and the results may be described descriptively by treatment group. Additionally, subgroup analyses may be performed by baseline variants.

6.17. Annual Report Analyses

Based on regulatory requirements for the Development Safety Update Report (DSUR), reports will be produced (if not already available from the study CSR) for the reporting period covered by the DSUR.

6.18. Clinical Trial Registry Analyses

Additional analyses will be performed for the purpose of fulfilling the Clinical Trial Registry (CTR) requirements.

Analyses provided for the CTR requirements include the following:

- Summary of AEs provided as a dataset which will be converted to an XML file. Both SAEs and 'Other' AEs are summarized: by treatment group, by MedDRA PT.
- An AE is considered 'Serious' whether or not it is a TEAE.
- An AE is considered in the 'Other' category if it is both a TEAE and is not serious. For each SAE and 'Other' AE, for each term and treatment group, the following are provided:
 - o the number of participants at risk of an event
 - o the number of participants who experienced each event term
 - o the number of events experienced.

- Consistent with www.ClinicalTrials.gov requirements, 'Other' AEs that occur in fewer than 5% of participants/subjects in every treatment group may not be included if a 5% threshold is chosen (5% is the minimum threshold).
- AE reporting is consistent with other document disclosures (e.g., the CSR, manuscripts, and so forth).

6.19. Analyses for the Open-Label Addendum Substudies

6.19.1. General Considerations

Data from participants in the substudies will be summarized separately from participants in the main PYAH study and separately for each addendum. The definition of study baseline and study time intervals will be the same as defined for the main study (see Sections 6.1.2 and 6.1.3). Additionally, the handling of dropouts and missing data will be similar to that described for the main study (see Section 6.3) with the exception of the mixed-effects model for repeated measures, as the data from the substudy will not include inferential analyses.

This table defines the populations for the analysis of the substudies.

Population	Description	
Entered - Addendum	Definition : All participants who sign the informed consent form for the	
	addendum.	
	Purpose: Used for disposition analysis.	
	Treatment Groups: None	
	Inferential Comparisons: None	
Efficacy - Addendum	Definition : All participants who were allocated and received study intervention	
	in the addendum and provided at least one postbaseline measure for the relevant	
	endpoint. Participants will be analyzed according to the intervention to which	
	they were allocated (intention to treat).	
	Purpose: Used for efficacy and pharmacodynamic variables analyses.	
	Treatment Groups (Short Label):	
	Addendum (2):	
	700 mg LY3819253, 15-minute infusion (700 LY, 15-min), 700 mg	
	LY3819253 and 1400 mg LY3832479, 30-minute infusion rate	
	(700/1400 LY/LY2, 30-min), 700 mg LY3819253 and 1400 mg	
	LY3832479, 15-minute infusion rate (700/1400 LY/LY2, 15-min).	
	CCI	
	Addendum (4):	
	Arm A – intravenous (IV)	
	• 70 mg LY3853113, 140 mg/min (Dose A-1), placebo (Dose A-1	
	Pbo)	
	 175 mg LY3853113, 140 mg/min (Dose A-2a), placebo (Dose A- 	

2a Pbo)

- 175 mg LY3853113, 350 mg/min (Dose A-2b), placebo (Dose A-2b Pbo)
- 175 mg LY3853113 + 700 mg LY3819253 + 1400 mg LY3832479, 350 mg/min (Dose A-2c), placebo (Dose A-2c Pbo)
- 1750 mg LY3853113, 350 mg/min (Dose A-3), placebo (Dose A-3 Pbo)
- Arm B subcutaneous (SC)
 - 280 mg LY3853113 (Dose B-1), placebo (Dose B-1 Pbo)
 - 560 mg LY3853113 (Dose B-2), placebo (Dose B-2 Pbo)

Additional optional arms may be added if decided.

Inferential Comparisons: None

Safety - Addendum

Definition: All participants allocated to treatment in the addendum and who received study intervention. Participants will be analyzed according to the intervention they actually received.

Purpose: Used for safety analyses, analyses of COVID-19-related hospitalization or death from any cause.

Treatment Groups (Short Label):

Addendum (2):

700 mg LY3819253, 15-minute infusion (700 LY, 15-min), 700 mg LY3819253 and 1400 mg LY3832479, 30-minute infusion rate (700/1400 LY/LY2, 30-min), 700 mg LY3819253 and 1400 mg LY3832479, 15-minute infusion rate (700/1400 LY/LY2, 15-min).

CL

- Arm A intravenous (IV)
 - 70 mg LY3853113, 140 mg/min (Dose A-1), placebo (Dose A-1 Pbo)
 - 175 mg LY3853113, 140 mg/min (Dose A-2a), placebo (Dose A-2a Pbo)
 - 175 mg LY3853113, 350 mg/min (Dose A-2b), placebo (Dose A-2b Pbo)
 - 175 mg LY3853113 + 700 mg LY3819253 + 1400 mg LY3832479, 350 mg/min (Dose A-2c), placebo (Dose A-2c Pbo)
 - 1750 mg LY3853113, 350 mg/min (Dose A-3), placebo (Dose A-3 Pbo)
- Arm B subcutaneous (SC)
 - 280 mg LY3853113 (Dose B-1), placebo (Dose B-1 Pbo)
 - 560 mg LY3853113 (Dose B-2), placebo (Dose B-2 Pbo)

Additional optional arms may be added if decided.

Inferential Comparisons: None

Pharmacokinetic - Addendum **Definition**: All participants who were allocated and received study intervention in the addendum and have evaluable pharmacokinetic sample. Participants will be analyzed according to the intervention they received. Purpose: Used for pharmacokinetic analyses. Treatment Groups (Short Label): Addendum (2): 700 mg LY3819253, 15-minute infusion (700 LY, 15-min), 700 mg LY3819253 and 1400 mg LY3832479, 30-minute infusion rate (700/1400 LY/LY2, 30-min), 700 mg LY3819253 and 1400 mg LY3832479, 15-minute infusion rate (700/1400 LY/LY2, 15-min). Addendum (4): Arm A – intravenous (IV) 70 mg LY3853113, 140 mg/min (Dose A-1), placebo (Dose A-1 • 175 mg LY3853113, 140 mg/min (Dose A-2a), placebo (Dose A-175 mg LY3853113, 350 mg/min (Dose A-2b), placebo (Dose A-• 175 mg LY3853113 + 700 mg LY3819253 + 1400 mg LY3832479, 350 mg/min (Dose A-2c), placebo (Dose A-2c Pbo) • 1750 mg LY3853113, 350 mg/min (Dose A-3), placebo (Dose A-3 Pbo) Arm B – subcutaneous (SC) 280 mg LY3853113 (Dose B-1), placebo (Dose B-1 Pbo) 560 mg LY3853113 (Dose B-2), placebo (Dose B-2 Pbo) Additional optional arms may be added if decided. Inferential Comparisons: None

Participant disposition will be summarized by treatment group and infusion rate and/or administration route in a similar manner as the main study (see Section 6.6).

Participant characteristics will be summarized by treatment group and infusion rate and/or administration route in a similar manner as the main study (see Section 6.7).

Treatment compliance will be summarized by treatment group and infusion rate and/or administration route in a similar manner as the main study (see Section 6.8).

Prior medication(s) and concomitant therapies summarized by treatment group and infusion rate and/or administration route in a similar manner as the main study (see Section 6.9).

The primary objective for the substudies is to characterize the safety and tolerability of LY3819253 alone, and in combination with LY3832479; and LY3853113 alone, and in

combination with LY3819253 and LY3832479. Safety endpoints include safety assessments such as AEs and SAEs. All safety analyses will be summarized by treatment group and infusion rate and/or administration route in a similar manner as the main study (see Section 6.12).

The secondary PK objective for the substudies is to characterize the PK of LY3819253 alone, and in combination with LY3832479 and LY3853113 alone, and in combination with LY3819253 and LY3832479. The secondary PK endpoint is mean concentration of LY3819253 alone, and in combination with LY3832479 and LY3853113 alone, and in combination with LY3819253 and LY3832479 on Day 29. The PK endpoint will be summarized by treatment group and infusion rate and/or administration route in a similar manner as the main study (see Section 6.11).

The secondary efficacy objective for the substudies is to characterize the SARS-CoV-2 viral load and viral clearance for participants who received LY3819253 alone, and in combination with LY3832479; and LY3853113 alone, and in combination with LY3819253 and LY3832479. The following are the secondary efficacy endpoints:

- Change from baseline in SARS-CoV-2 viral load to:
 - o Day 3
 - o Day 5
 - o Day 7
 - o Day 11
- Proportion of participants with viral load greater than 5.27 on Day 7
- Time to SARS-CoV-2 clearance
- SARS-CoV-2 viral load AUC assessed through Day 11
- For addendum (2) CCI
 - o Proportion of participants with viral load greater than 5.27 on Day 7 among participants enrolled with ≤8 days of symptoms prior to randomization
 - Proportion of participants that achieve SARS-CoV-2 clearance (Days 3, 5, 7, 11, and 29)

The secondary efficacy endpoints will be summarized by treatment group and infusion rate and administration, as appropriate, in a similar manner as the main study (see Section 6.10).

The exploratory efficacy objectives for the substudies are to characterize overall participant clinical status, viral load, and symptom resolution and improvement. The following are the exploratory efficacy endpoints:

- For addendum (2) CCI
 - Proportion (percentage) of participants who experience these events by Day 22,
 29, 60, and 85
 - COVID-19 related hospitalization (defined as ≥24 hours of acute care)
 - Death from any cause
 - o Proportion (percentage) of participants who experience these events by Day 29
 - COVID-19 related hospitalization (defined as ≥24 hours of acute care),
 - COVID-19 related emergency room visit, or

- Death from any cause
- Time to symptom resolution
- o Proportion of participants demonstrating symptom resolution via the symptom questionnaire on Days 3, 5, 7, 11, 22, and 29
- o Change in symptom score (total of ratings) from baseline up to Days 7, 11, 22, and 29.
- Time to symptom improvement
- o Proportion of participants demonstrating symptom improvement via the symptom questionnaire on Days 3, 5, 7, 11, 22, and 29
- For addendum (4):
 - Duration, in days, of hospitalizations,
 - o Proportion of participants admitted to the ICU
 - o Proportion of participants requiring mechanical ventilation
 - o Proportion of participants that achieve SARS-CoV-2 clearance (Days 3, 5, 7, 11, and 29)
 - o 75th percentile of SARS-CoV-2 viral load at Day 7
 - Characterize emergence of viral resistance to LY3853113

The exploratory efficacy endpoints will be summarized by treatment group and infusion rate and/or administration route in a similar manner as the main study (see Section 6.10).

Additional analyses may be performed for the substudies.

An interim analysis of safety data may be conducted at any time for participants who have reached Day 3.

7. References

Firth D. Bias reduction of maximum likelihood estimates. *Biometrika*. 1993;80(1):27-38. https://doi.org/10.2307/2336755

8. Appendices

